4.2 Masking and Unmasking

The study statistician will generate the complete randomized study drug kit list. The subject, Sponsor, Investigators, and study staff will be masked during the randomization process and throughout the study.

[REDACTED]
[REDACTED].
If unmasking of a subject becomes critical to the subject's safety, the Principal Investigator must authorize such decision. If possible, such decision must be first consulted with both the study Sponsor and the Medical Monitor. Unmasking can be achieved by opening the sealed envelope that corresponds to the randomization number assigned to the subject. The Sponsor and the Medical Monitor must be notified within 24 hours following an emergency unmasking of any subject.

5 Sample Size and Power Considerations

The sample size was not calculated to yield pre-stated power for a specific efficacy analysis; instead, the sample size in this early phase study will assist in obtaining estimates from which to power future studies.

6 Data Preparation

6.1 Input Data

All reported study data will be recorded on the eCRF [REDACTED] [REDACTED]. Only the Principal Investigator and authorized study staff according to the Delegation of Responsibilities log are entitled to make entries in the eCRF.

After data are entered into the clinical study database, electronic edit checks and data review will be performed. All data validation specifications and procedures are detailed in the Data Validation Manual as a separate document. When the database has been declared to be complete and accurate, the database will be locked. Any changes to the database after data have been locked can only be made with the approval of the Sponsor [REDACTED]

All analyses outlined in this document will be carried out after the following have occurred:

- All data management requirements are met according to [REDACTED] standard operating procedures, including data entry, performance of edit and validation checks, documentation and resolution of data queries, and database lock with written authorization provided by [REDACTED] Sponsor personnel.
- Protocol deviations have been identified and status defined (major/minor deviations).
- Analysis populations have been determined.
- Randomized treatment codes have been unmasked.

Please note that the database must be locked and all protocol deviations adjudicated as either major or minor prior to unmasking.

6.2 Output Data

Data will be transferred to [REDACTED] and incorporated into standard formats following the Study Data Tabulation Model (SDTM). Data will then be mapped to analysis datasets using the Analysis Data Model (ADaM). Both SDTM- and ADaM-formatted data will be used to create the subject listings, while all tables and figures will be based on the ADaM-formatted data.

[REDACTED]
[REDACTED]
[REDACTED]
[REDACTED]
[REDACTED]
[REDACTED]

7 Analysis Populations

7.1 Intent-to-Treat

The intent-to-treat (ITT) population includes all randomized subjects. All efficacy analyses will be performed on the ITT population, and subjects will be analyzed as randomized.

7.2 Per Protocol

The per-protocol (PP) population includes subjects in the ITT population who do not have significant protocol deviations likely to seriously affect the efficacy measures of the study. Protocol deviations will be assessed prior to database lock and unmasking. Subjects in the PP population will be analyzed as treated. The t-test analyses on the composite score of eyelid margin redness, eyelid debris, and eyelid discomfort will be conducted using the PP population as an additional analysis to assess efficacy when subjects strictly comply with the protocol. In the event that the ITT and PP populations are the same, this analyses will not be performed.

7.3 Safety

The Safety population includes all randomized subjects who have received at least one dose of the investigational product. Subjects in the Safety population will be analyzed as treated.

8 General Statistical Considerations

8.1 Unit of Analysis

The unit of analysis for the final analysis in this study will be the study eye, fellow eye, and both eyes for all summaries of efficacy and ocular safety assessments performed by eye (VA, SLE, IOP, dilated ophthalmoscopy). The study eye will be the eye with the highest composite score in Eyelid Margin Redness, Eyelid Debris, and Eyelid Discomfort [REDACTED] at the Baseline/Day 1 study visit, or the right eye (OD) if both eyes of a subject have the same score at baseline. The contralateral eye will be considered as the fellow eye; however, no analyses will be conducted specifically for the contralateral eyes. Instead as stated above, analyses by both eyes will be conducted given the bilateral nature of the dosing and the inclusion criteria requiring both eyes to qualify. Additionally, AEs, medical history, and concomitant medications will be presented at the subject level.

8.2 Missing or Inconclusive Data Handling

Efficacy analyses will be primarily based on the ITT population with observed data only. To check for robustness of outcomes, missing data will be imputed using last time consistent (pre- and post-eyelid scrub) observation carried forward for the composite endpoint analysis by eye.

AEs with completely missing onset dates will be considered treatment-emergent. AEs with a missing month and day of onset will be considered treatment-emergent unless the onset year is prior to the year of first dose of study treatment. AEs with a missing day of onset will be considered treatment-emergent unless (1) the onset year is prior to the first dose of study treatment or (2) the onset year is the same as the year of first dose of study treatment and the onset month is prior to the month of first dose of study treatment. AEs

missing a relationship will be considered treatment-related. Medications with missing start dates will be considered concomitant medications unless (1) the medication start year is prior to the year of the first dose of study treatment or (2) the medication start year is the same as the year of first dose of study treatment and the medication start month is prior to the month of first dose of study treatment, in which case these will be considered prior (and possibly concomitant depending on the end date) medications. Medications with missing end dates will be considered concomitant medications unless (1) the medication end year is prior to the year of first dose of study treatment or (2) the medication end year is the same as the year of first dose of study treatment and the medication end month is prior to the month of first dose of study treatment, in which case these will be considered prior medications. In the event that a medication end date is prior to the medication start date, the medication end date will be considered as one day after the medication start date for the purposes of determining whether this is a prior and/or concomitant medication. The actual reported AE onset dates and medication start and end dates, including any unknown portions, will be included in the appropriate listings as entered by site personnel.

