5. CONCOMITANT MEDICATION(S)

5.1 Previous and Concomitant Medication(s)

All non-ophthalmic medications (with the exception of isotretinoin or any other retinoids) used in the 3 months prior to the Screening Visit must be recorded. Additionally, isotretinoin or any other retinoids, and all ophthalmic medications used in the 12 months prior to the Screening Visit must be recorded. All medications used between the Screening Visit and the Day 28/Exit Visit must be recorded.

Any diagnostic ophthalmic agents administered throughout the study will not be captured in the concomitant medication log.

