11.2 Concomitant Medications

Concomitant medications will be coded using World Health Organization (WHO) Drug Dictionary (Global B3, March 2019) and summarized to the therapeutic drug class (Anatomical Therapeutic Chemical [ATC] 4 classification) and preferred name. If the ATC 4 classification is not provided, the next lowest classification that is provided in the coding dictionary will be used. The preferred name will be defined as the active ingredient; if the active ingredient is not provided or includes more than two ingredients (e.g., multivitamins)

then the drug name will be summarized as the preferred name. Any uncoded terms will be summarized under the ATC classification and preferred name of “Uncoded.”

Concomitant medications are defined as those medications listed as having been taken (1) prior to initiation of study drug administration and continuing for any period of time following the first administration of study drug or (2) at any time following the first administration of study drug.

Concomitant medications will be summarized using the ITT population separately for ocular and non-ocular data. Medications will be tabulated for each treatment group using frequencies and percentages. Subjects may have more than 1 medication per ATC text. At each level of subject summarization, a subject will be counted once if he/she reports 1 or more medications. Percentages will be based on the number of subjects in each treatment group. Listings of prior and concomitant medications will be generated separately for ocular and non-ocular medications.

12 Dosing Compliance and Treatment Exposure

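### SAP 8.2 classifies some partially dated medications and adverse events against the definitions in SAP 11.2 and 15.1, because it does not check the end date first

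*SAP*

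**What the plan says.** **Medications, start date missing (SAP 8.2).** "Medications with missing start dates will be considered concomitant medications unless" the known start year is before the first-dose year, or the start is in the first-dose year and its known month is before the first-dose month. Only for those exceptions does the end date enter: "in which case these will be considered prior (and possibly concomitant depending on the end date) medications".

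**Medications, end date missing (SAP 8.2).** The default is again concomitant, unless the known part of the end date falls in an earlier year or month than first dose.

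**Medications, end before start (SAP 8.2).** For this classification, "the medication end date will be considered as one day after the medication start date".

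**Adverse events (SAP 8.2).** "AEs with completely missing onset dates will be considered treatment-emergent". For year-only onset, "AEs with a missing month and day of onset will be considered treatment-emergent unless the onset year is prior to the year of first dose". If only the day is missing, the event is treatment-emergent unless the known year or month is earlier than that of first dose. No rule refers to resolution.

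**Definitions.** SAP 11.2 requires a concomitant medication to be taken after first dose, or to have been taken "prior to initiation of study drug administration and continuing for any period of time following the first administration of study drug". SAP 15.1 limits TEAEs to events that start or worsen from the day treatment begins, and keeps events that began earlier out of the summary tables.

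**Collection.** Protocol 5.1 states that "all ophthalmic medications used in the 12 months prior to the Screening Visit must be recorded". Protocol 10.5 records adverse events from consent, and Protocol 7.2 places Day 1 three to seven days after Screening.

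**The concern.** A partial-date rule is needed when the recorded dates leave the timing open. Here it also decides cases that the recorded dates already settle. If a stop or resolution date before first dose is on file, the unknown start no longer matters, yet SAP 8.2 puts the record on the on-treatment side. The impossible-end-date rule errs in the other direction: a demonstrably wrong end date gets a less cautious default than a missing one.

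The record type is plausible in this trial. Protocol 4.4 (criterion 14) has artificial tears stopped at least 24 hours, and other ophthalmic medicines at least 30 days, before Screening, and the look-back for eye medicines is 12 months. A subject may well know when a product was stopped but not when it was begun. Such records would enter the ocular concomitant medication table (14.1.6.1) as use during treatment. Events confined to the screening interval could enter the TEAE tables (14.3.1 to 14.3.5) of a study whose secondary objectives are safety and tolerability.

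**Working it through.** The plan gives no figure to reproduce. The check applies the SAP 8.2 rules literally and compares the result with the definitions. First dose is set at 20 May 2019, an illustrative date within the study period in the protocol synopsis.

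**(a) Medications with an incomplete start and a complete stop date**

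| Start recorded | Stop recorded | SAP 8.2 | SAP 11.2 |
|---|---|---|---|
| missing | 31 Mar 2019 | concomitant | prior |
| 2019 only | 31 Mar 2019 | concomitant | prior |
| May 2019 | 10 May 2019 | concomitant | prior |
| Apr 2019 | 10 May 2019 | prior | prior |
| 2018 only | 31 Mar 2019 | prior | prior |

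The first three rows conflict. The last two agree, because the exception consults the end date.

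The washout narrows the reach. A non-tear eye medicine that respects it stopped at least 30 + 3 = 33 days before first dose. No month exceeds 31 days, so its start month, if known, is always earlier than the first-dose month and the record is handled correctly. For these medicines only a wholly missing start, or the first-dose year alone, fails. Artificial tears need stop only 24 hours + 3 days = 4 days before first dose, so for them the same-month case can also arise.

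If both dates are partial, the missing-start and missing-end rules can give opposite answers, and no order between them is stated.

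**(b) Adverse events recorded as resolved on 17 May 2019**

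| Onset recorded | SAP 8.2 | SAP 15.1 |
|---|---|---|
| missing | TEAE | not TEAE |
| 2019 only | TEAE | not TEAE |
| May 2019 | TEAE | not TEAE |
| Apr 2019 | not TEAE | not TEAE |

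When only the day of onset is missing, the default applies if onset falls in the first-dose month. For onset k days before first dose, the share of 2019 calendar dates on which it does is (365 − 12k)/365:

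- k = 1: 353/365 = 97%
- k = 7: 281/365 = 77%

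So the exception for an earlier month seldom helps in the screening interval.

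**(c) End date before start date**

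For a start k days before first dose, the assigned end falls k − 1 days before first dose.

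- k = 0 or 1: the assigned end is on or after the day of first dose, so the record is concomitant.
- k of 2 or more: the assigned end is at least one day before first dose, so the record is prior only.
- For the same start with a missing end date: concomitant at every k.

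**Weight of one record.** Planned groups are about 10, 5, 10 and 10. One subject is 1/10 = 10 points or 1/5 = 20 points. In the pooled groups of about 20 active and 15 placebo (SAP 17), it is 1/20 = 5 or 1/15 = 6.7 points.

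**After the fix.** Checking the end date first makes the three conflicting medications prior and the three conflicting events non-TEAE. Treating an impossible end date as missing makes those records concomitant by default.

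**The case against.** **The definitions already govern.** With a complete pre-dose stop date nothing needs imputing, and a programmer following SAP 11.2 or 15.1 would reach the right class. That may happen, but SAP 8.2 states an explicit contrary rule and the SAP does not say which section prevails.

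**The defaults are conservative.** Calling an event of unknown onset treatment-emergent is sound safety practice, and this stands where timing is truly unknown. It does not justify overriding a recorded resolution before dosing.

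**Cleaning will catch it.** SAP 6.1 requires edit checks and query resolution before lock. This largely stands for impossible end dates, and with only three to seven days between consent and dosing, missing onsets for resolved events should be rare. The SAP nevertheless wrote a rule for records that survive cleaning. That rule does harm only if the end date is the wrong entry.

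**AE resolution dates may not be collected.** The documents do not say explicitly that they are, so part (b) applies only where they exist.

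Four stronger readings are tempting and not supported:

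- *Every unknown-start medicine stopped before dosing is misclassified.* Records whose known start month or year precedes first dose are handled correctly.
- *False concomitant entries lead to per-protocol removal.* No section derives deviations from this classification. Protocol 9 has sites record deviations and the sponsor classify them, and SAP 6.1 has them adjudicated before unmasking.
- *Prohibited use can be concealed.* A medicine can drop out of the summary table, but SAP 8.2 keeps its dates as entered in the listings.
- *The number of false records can be estimated.* The documents give neither the number of prior medicines per subject nor the share with missing starts.

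**Conclusion.** The point holds as a conflict between stated rules, limited to three record types:

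- medications with an uninformative start and a recorded pre-dose stop;
- adverse events with an uninformative onset and a recorded pre-dose resolution;
- medications with an end before the start that began at least two days before first dose.

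The first two are counted on the on-treatment side against SAP 11.2 and 15.1. The third is moved off it, with a weaker safeguard than a missing date receives. Only the concomitant-medication and TEAE summaries are affected; the composite score and the efficacy comparisons are untouched. The number of records is unknown and may be small, but at these group sizes a single subject is visible in a percentage. The conclusion rests on a literal reading of SAP 8.2 and, for events, on resolution dates being collected.

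**What to change.** Amend SAP 8.2 before lock:

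1. Check the end date first. A medication whose full end date, or the known part of it, precedes first dose is prior, whatever its start date.
2. An adverse event whose resolution date, where collected, precedes first dose is not treatment-emergent.
3. If an end date before the start date remains unresolved after querying, treat the end date as missing and apply the missing-end-date rule in place of start plus one day. This step must run before step 1, so that an impossible end date cannot itself make the record prior. It accepts some over-counting, in line with the existing default.
4. Keep the present defaults for all other records.

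The cost is a few sentences in the SAP and a small change to the derivation programs. No new data are needed, except that step 2 depends on AE resolution dates being on the eCRF.

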8.3 Definition of Baseline

Eyelid signs and symptoms (Eyelid discomfort, Eyelid Margin Redness and Eyelid Debris) were conducted [REDACTED]. The analysis of the response to treatment of eyelid signs and symptoms will involve comparisons against the [REDACTED] baseline assessments. For all other assessments [REDACTED] the Baseline measure will be defined as the last non-missing measure prior to initiation of study treatment.

8.4 Data Analysis Conventions

The final analysis including Cohorts 1 and 2 will be performed [REDACTED] after the study is completed and the database has been locked and released for unmasking of Cohort 2, and the statistical analysis plan has been finalized. [REDACTED]

In addition, the final analysis will pool results from both Cohort 1 and Cohort 2 for some endpoints as applicable. Data to be pooled includes the following:

- Subject Disposition
- Demographics
- Baseline Characteristics

Statistical programming and analyses will be performed using SAS® Version 9.4 or higher. Output will be provided in rich text format (RTF) for tables and portable document format (PDF) for tables, listings, and figures using landscape orientation. All study data will be listed by subject, treatment, and visit (as applicable) based on all randomized subjects unless otherwise specified.

Change from baseline will be provided as summaries for continuous and ordinal efficacy (Eyelid Margin Redness, Eyelid Debris, and Eyelid Discomfort, along with the composite scores; [REDACTED]
[REDACTED]
[REDACTED]

[REDACTED]. Summaries for continuous variables will include the number of observations (n), arithmetic mean, standard deviation (SD), standard error of the mean (SEM), median, minimum, and maximum. Minima and maxima will be reported with the same precision as the raw values; means and medians will be presented to one additional decimal place than reported in the raw values. Standard deviations and standard errors of the mean will be presented to two additional decimal places than reported in the raw values. Summaries for discrete and ordinal efficacy (Eyelid Margin Redness, Eyelid Debris, and Eyelid Discomfort, along with the composite score) variables will include frequency counts and percentages. All percentages will be rounded to one decimal place (i.e., XX.X%). For continuous variables, the differences between active treatment groups and placebo will be calculated as Active – Placebo using descriptive statistics and two-sample Student's t-distribution CIs and p-values. Within one group, change from baseline will be calculated as Follow-up Visit – Baseline using descriptive statistics and one-sample Student's t-distribution CIs and p-values; differences in mean change from baseline scores between treatment groups will be summarized including 95% t-distribution CIs around the differences in mean. Summaries will be presented for each post-baseline visit. These summaries will be completed separately for the pre-scrub and post-scrub assessments. For discrete variables, binomial proportions and Clopper-Pearson CIs will be used to compare follow-up visit to baseline within each treatment group; Fisher's Exact Test will be used to compare the categorical endpoints between treatment groups.

All assessments will be summarized by study eye, fellow eye, and by both eyes, unless specifically stated. When the assessments need to be presented in both eyes, for continuous variables, between group CIs and p-values will come from a mixed effects linear model for each post-baseline visit

Confidence intervals (CI) for differences between treatment groups will be two-sided at 95% confidence. P-values may also be presented for change from baseline values, however the study is not powered to show significance for these.

Unless otherwise specified, summaries will be presented by treatment group and, where appropriate, visit.

8.5 Adjustments for Multiplicity

No adjustments for multiplicity will be made for this early phase study.

9 Disposition of Subjects

Subject disposition will be presented in terms of the numbers and percentages of subjects who were randomized, completed the study, and discontinued from the study. Subjects who complete the Day 28/Exit Visit will be considered study completers. Disposition will be summarized by treatment group and for all subjects.

The total number of screened subjects with the number and percentage of screen failure subjects. The reasons for screen failure will be displayed with the percentages calculated using total number of screen failures as the denominator. The number of subjects in each of the analysis populations (ITT, PP, and Safety) will be displayed by treatment and percentages will be calculated using randomized subjects as the denominator.

The number and percentage of subjects prematurely discontinued from the study and the reasons for study discontinuation will be summarized by treatment group for all randomized subjects. The reasons for study discontinuation that will be summarized include: AE, lost to follow-up, physician decision, protocol violation, study terminated by Sponsor, withdrawal by subject, and other. A subject listing will be provided that includes the date of and reason for premature study discontinuation and masking/unmasking information.

The number and percentage of subjects with major protocol deviations will be summarized by treatment group for all randomized subjects. The protocol deviations that will be summarized include: informed consent, inclusion/exclusion and randomization, test article/study drug instillation and assignment at site, improper protocol procedures at site (missed, repeated, no per protocol), site's failure to report serious adverse event (SAE)/AE, visit out of window, subject's non-compliance with test article/study drug, subject's use of prohibited concomitant medication, subject's failure to follow instructions, and other. A subject listing will be provided that includes the date of the deviation, the deviation code, the deviation description, and the classification of whether the deviation was judged to be major or minor.

In addition, subject listings will be provided that include informed consent date, inclusion and exclusion criteria violations, and exclusions from each population.

10 Demographic and Pre-treatment Variables

